8.6.4 Diarrhea

Antidiarrheal medication per standard practice is recommended at the first sign of abdominal cramping, loose stools or overt diarrhea.

At first bout of diarrhea:

- Initiate loperamide: initial dose of 4 mg (2 tablets/capsules) with the first bout of diarrhea followed by 2 mg (1 tablet/capsule) every 4 hours or after every unformed stool (maximum 16 mg a day) and continue loperamide at this frequency until diarrhea free for 12 hours.

For persistent Grade 1 diarrhea on loperamide:

- Add Lomotil (diphenoxylate hydrochloride and atropine sulfate) 1 tablet (2.5 mg) every 6 hours to 8 hours

For persistent Grade 2:

- Consider adding octreotide (short-acting) 150 μ g SC TID; or after initial dose of short-acting octreotide, if well tolerated, a single dose of octreotide LAR 20 mg IM

For Grade 3:

- Administer octreotide (100-150 μ g SC BID or IV (25-50 μ g/h) if dehydration is severe, with dose escalation up to 500 μ g SC TID).
- Use IV fluids as appropriate.
- Consider prophylactic antibiotics as needed (eg, fluoroquinolones) especially if diarrhea is persistent beyond 24 hours or there is fever or Grade 3-4 neutropenia.

8.6.5 Management of hyperlipidemia and hyperglycemia

Treatment of hyperlipidemia should take into account the pre-treatment status and dietary habits. If blood lipid levels exceed the thresholds identified in eligibility

criterion 4.2.13 and treatment of hyperlipidemia is being considered, further blood tests to monitor hyperlipidemia must be taken in the fasting state.

Hypercholesterolemia (> 300 mg/dL or 7.75 mmol/L) or hypertriglyceridemia (>2.5 x ULN) should be treated with a 3-hydroxy-3-methyl-glutaryl (HMG)-CoA reductase inhibitor (e.g., atorvastatin, pravastatin) or appropriate lipid-lowering medication, in addition to diet. Patients should be monitored clinically and through serum biochemistry for the development of rhabdomyolysis and other adverse events as required in the product label/data sheets for HMG-CoA reductase inhibitors.

Note: Concomitant therapy with fibrates and an HMG-CoA reductase inhibitor is associated with an increased risk of a rare but serious skeletal muscle toxicity manifested by rhabdomyolysis, markedly elevated creatine kinase (CPK) levels and myoglobinuria, acute renal failure and sometimes death. The risk versus benefit of using this therapy should be determined for individual patients based on their risk of cardiovascular complications of hyperlipidemia.

Grade 3 **hyperglycemia** has been observed in patients receiving EVE therapy. In many cases in study EVE C2222, the affected patients had an abnormal fasting glucose at baseline. Based on this finding, it is suggested that optimal glucose control should be achieved before starting a patient on EVE and should be monitored during EVE therapy.

8.6.6 Management of non-infectious pneumonitis

Both asymptomatic radiological changes (grade 1) and symptomatic non-infectious pneumonitis (grade 2 = not interfering with activities of daily living or grade 3 = interfering with activities of daily living and oxygen indicated) have been noted in patients receiving EVE therapy. Non-infectious pneumonitis has been associated with EVE and other mTOR inhibitors (Atkins 2004). In order to monitor for asymptomatic (grade 1) pulmonary infiltrates, a chest X-ray is required if a CT scan of chest is not used for bi-monthly disease evaluations. Additional chest CT scans may be performed, when clinically necessary. If non-infectious pneumonitis develops, a consultation with a pulmonologist should be considered. If the patient develops grade 3 pneumonitis, treatment with EVE should be interrupted and the patient should be treated as medically indicated (short course corticosteroids, oxygen, etc).

Management of non-infectious pneumonitis suspected to be associated with EVE and dose modifications instructions are provided below.

Table 4: Management of non-infectious pneumonitis

Worst Grade Pneumonitis	Required Investigations	Management of Pneumonitis	EVE Dose Adjustment
Grade 1	CT scans with lung windows and pulmonary function testing including: spirometry, DLCO, and room air O₂ saturation at rest. Repeat chest x-ray/CT scan every 2 Cycles until return to baseline.	No specific therapy is required	Administer 100% of EVE dose.
Grade 2	CT scan with lung windows and pulmonary function testing including: spirometry, DLCO, and room air O₂ saturation at rest. Repeat each subsequent Cycle until return	Symptomatic only. Prescribe corticosteroids if cough is troublesome.	Reduce EVE dose until recovery to ≤ Grade 1. EVE may also be interrupted if symptoms are troublesome. Patients will be withdrawn from the study if they fail to

Worst Grade Pneumonitis	Required Investigations	Management of Pneumonitis	EVE Dose Adjustment
	to baseline. Consider bronchoscopy *		recover to ≤ Grade 1 within 3 weeks.
Grade 3	CT scan with lung windows and pulmonary function testing including: spirometry, DLCO, and room air O₂ saturation at rest.; Repeat each subsequent Cycle until return to baseline. Bronchoscopy is recommended *	Prescribe corticosteroids if infective origin is ruled out. Taper as medically indicated.	Hold treatment until recovery to ≤ Grade 1. May restart protocol treatment within 2 weeks at a reduced dose (by one level) if evidence of clinical benefit. Patients will be withdrawn from the study if they fail to recover to ≤ Grade 1 within 2 weeks.
Grade 4	CT scan with lung windows and required pulmonary function testing includes: spirometry, DLCO, and room air O₂ saturation at rest. Repeat each subsequent Cycle until return to baseline. Bronchoscopy is recommended *.	Prescribe corticosteroids if infective origin is ruled out. Taper as medically indicated.	Discontinue treatment.

***A bronchoscopy with biopsy and/or bronchoalveolar lavage is recommended.**

8.6.7 Wound healing complications

Impaired wound healing is a class effect of rapamycin derivatives, including everolimus. Caution should therefore be exercised with the use of Afinitor in the peri-surgical period.

8.6.8 Management of hypophosphatemia

Hypophosphatemia is a known side effect of EVE and will be monitored for patients receiving EVE. The CTCAE v4 grading of hypophosphatemia appears to be incompatible with the HUP laboratory's reference range. The HUP lab's LLN is 2.4 mg/dL. Grade 1 is <LLN – 2.5 mg/dL (which is N/A), Grade 2 is <2.5 – 2.0 mg/dL, Grade 3 is <2.0 – 1.0 mg/dL. Thus, a subject's phosphorus could be just 0.1 mg/dL below normal be considered a Grade 2 by the CTCAE v4. Therefore, while this protocol will still use the CTCAE v4 for grading purposes, we have instituted the guidelines outlined below for the management of hypophosphatemia. (It is noted that the CTCAE v5 has revised the hypophosphatemia grading guidelines.)

Hypophosphatemia should be managed with supplementation/oral replacement therapy as clinically indicated, at the discretion of the PI/treating physician. Events of hypophosphatemia, even if Grade 3 by the CTCAE v4 will not be subject to the EVE dose modification guidelines for non-hematological toxicity outlined in Table 11. EVE should be interrupted only if the hypophosphatemia event is severe or medically significant as determined by the PI/treating physician and/or if hospitalization or prolongation of existing hospitalization is indicated (these are the Grade 3 criteria in CTCAE v5).

8.6.9 Management of Hepatitis reactivation/flare

In cancer patients with hepatitis B, whether carriers or in chronic state, use of antivirals during anticancer therapy has been shown to reduce the risk of hepatitis B virus (HBV) reactivation and associated HBV morbidity and mortality (Loomba et al.

2008).

8.6.9.1 Monitoring and prophylactic treatment for hepatitis B reactivation

Table 5 provides details of monitoring and prophylactic therapy according to the baseline results of viral load and serologic markers testing.

Table 5: Action to be taken for positive baseline hepatitis B results

Test	Result	Result	Result	Result	Result
HBV-DNA	+	+ or -	-	-	-
HBsAg	+ or -	+	-	-	-
HBs Ab	+ or -	+ or -	+ and no prior HBV vaccination	+ or -	- or + with prior HBV vaccinati on
HBc Ab	+ or -	+ or -	+ or -	+	-
Recom- mendation	Prophylaxis treatment should be started 1-2 weeks prior to first dose of study drug Monitor HBV-DNA approximately every 6 weeks		No prophylaxis Monitor HBV-DNA approximately every 3 weeks		No specific action

Antiviral prophylaxis therapy should continue for at least 4 weeks after last dose of study drug. For hepatitis B reactivation, definition and management guidelines, see Table 6.

Table 6: Action to be taken in event of Hepatitis Reactivation

HBV reactivation (with or without clinical signs and symptoms)*	
For patients with baseline results: Positive HBV-DNA OR positive HBsAg ----- reactivation is defined as: [Increase of 1 log in HBV-DNA relative to baseline HBV-DNA value OR new appearance of measurable HBV-DNA]	Treat: Start a second antiviral AND Interrupt study drug administration until resolution: ≤ baseline HBV-DNA levels If resolution occurs within ≤ 28 days, study drug should be re-started at one dose lower, if available. If the patient is already receiving the lowest dose of study drug according to the protocol, the patient should restart at the same dose after resolution. Both antiviral therapies should continue at least 4 weeks after last dose of study drug. If resolution occurs > 28 days, patients should discontinue study drug but continue both antiviral therapies at least 4 weeks after last dose of study drug.
For patients with baseline results: Negative HBV-DNA and HBsAg AND [Positive HBs Ab (with no prior history of vaccination against HBV), OR positive HBc Ab] ----- reactivation is defined as: New appearance of measurable HBV-DNA	Treat : Start first antiviral medication AND Interrupt study drug administration until resolution: ≤ baseline HBV-DNA levels If resolution occurs within ≤ 28 days study drug should be re-started at one dose lower, if available. If the patient is already receiving the lowest dose of study drug according to the protocol, the patient should restart at the same dose after resolution. Antiviral therapy should continue at least 4 weeks after last dose of study drug.

	If resolution occurs > 28 days, patients should discontinue study drug but continue antiviral therapy at least 4 weeks after last dose of study drug.
--	---

* All reactivations of hepatitis B are to be recorded as grade 3 (CTCAE v 3.0 Metabolic Laboratory/Other: Viral Re-activation), unless considered life threatening by the investigator; in which case they should be recorded as grade 4 (CTCAE v 3.0 Metabolic Laboratory/Other: Viral Re-activation). Date of viral reactivation is the date on which **both** DNA and ALT criteria were met (e.g. for a patient who was HBV-DNA positive on 01-JAN-10 and whose ALT reached $\geq 5 \times$ ULN on 01-APR-10, the date of viral reactivation is 01-APR-10).

8.6.9.2 Monitoring for Hepatitis C Flare

The following two categories of patients should be monitored every 6 weeks for HCV reactivation:

1. Patients with detectable HCV RNA-PCR test at baseline.
2. Patients known to have a history of HCV infection, despite a negative viral load test at baseline (including those that were treated and are considered 'cured')

For definition of hepatitis C reactivation and the management guidelines, see Table 3-4 Guidelines for management of hepatitis C.

Table 7: Guidelines for management of hepatitis C

HCV flare*	
For patients with baseline results: Detectable HCV-RNA, HCV flare is defined as: 2 log ₁₀ IU/mL increase in HCV-RNA AND ALT elevation x 5 ULN or 3 baseline level, whichever is higher	Discontinue study drug
For patients with baseline results: Knowledge of past hepatitis C infection with no detectable HCV-RNA, HCV flare is defined as: New appearance of detectable HCV-RNA AND ALT elevation x 5 ULN or 3 baseline level, whichever is higher	Discontinue study drug

* All flares of hepatitis C are to be recorded as grade 3 (CTCAE v3.0 Metabolic Laboratory/Other: Viral Flare), unless considered life threatening by the investigator; in which case they should be recorded as grade 4 (CTCAE v 3.0 Metabolic Laboratory/Other: ViralFlare).

8.7 Dose Delays

Treatment should be delayed for major events if HCQ or EVE may further complicate the major event. "Major events" are non treatment-related grade 3 and 4 hematologic and non-hematologic toxicities. If a major event requires a delay of treatment, treatment must be delayed until toxicity is resolved (\leq Grade 1 or \leq Baseline). If toxicity is not resolved in \leq 4 weeks (28 days), treatment will be discontinued (see Section 7.8).

8.8 Dose Modifications

For patients who are unable to tolerate the protocol-specified dosing

schedule, dose adjustments are permitted in order to keep the patient on study drug. Dose modification guidelines are found in the sections below. Any consideration to deviate from these protocol-defined dose modification guidelines should be discussed with the Principal Investigator and treating physician for approval or disapproval in advance. Since this is a pilot study, this protocol allows physician discretion surrounding dose adjustment decisions. Dose adjustment decisions based on PI/physician discretion must be documented as such.

Because nausea, vomiting, diarrhea or rash may be attributable to either HCQ or EVE, Table 8 outlines the order in which to dose reduce one or the other agent. All other toxicities should be managed with dose modification of EVE alone.

Table 8: Guidelines for Selecting Agent for Dose Reduction if Overlapping Toxicities

Overlapping Toxicity	Dose Reduce First	Dose Reduce Second
Rash	EVE	HCQ
Nausea	HCQ	EVE
Anorexia	HCQ	EVE
Diarrhea	EVE	HCQ

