8.8.1 Hydroxychloroquine Dose Modification

Any AE of \geq Grade 3 and attributed as possibly, probably or definitely related to HCQ will result in the dose being held until the AE has resolved to \leq grade 1 or baseline while EVE dosing may continue uninterrupted. If the AE resolves, reinstatement of treatment can occur but at a reduced dose as described in Table 9. If the AE recurs at the reduced dose, treatment will be held until the AE has resolved to \leq grade 1 and when resolved treatment can be reinstated at the next lower dose level. No more than 2 dose reductions are allowed during the maintenance cycles.

Table 9: Hydroxychloroquine Dose Reduction Schema

Dose Level	Dose mg/day	Reduce to
-2	400 mg twice daily	400 mg daily
-1	600 mg am and 400 mg pm	400 mg twice daily
1	600 mg twice daily	600 mg am and 400mg pm

If any AEs occur at grade \leq 2 that are attributed as possibly, probably or definitely related to HCQ, HCQ may be continued and the AE managed with supportive care, with the exception of visual field deficit. **Visual field deficit is a potential symptom of peripheral retinal toxicity should prompt drug discontinuation and ophthalmologic evaluation immediately. With particular regard to visual field deficits patients should be cautioned to report any visual symptoms, particularly difficulty seeing entire words or faces, intolerance to glare, decreased night vision, or loss of peripheral vision.**

If any AEs occur at grade \leq 2 that are attributed as possibly, probably or definitely related to HCQ, HCQ may be interrupted if the toxicity is either intolerable to the patient or PI/physician discretion determines it is in the best interest of the patient. In such cases, HCQ should be interrupted until recovery to grade \leq 1. If

resolution occurs in ≤ 7 days HCQ may be reintroduced at the same dose. If resolution takes > 7 days HCQ should be reintroduced at the lower dose level. If the event returns to grade 2, then HCQ should be interrupted until recovery to grade ≤ 1 , after which HCQ should be reintroduce at the lower dose level.

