8.8.1.1 Management of suspected HCQ induced myopathy

Myopathy leading to muscle weakness is a rare but potentially serious side effect of HCQ. In our experience, this toxicity resolves with holding drug and can be reduced by reducing dose. With close attention to early signs of this toxicity, the goal is for it to be managed before it becomes serious and reaches a higher grade. Therefore, in the instance of grade >1 muscle weakness and/or elevated CPK or at MD discretion (even if the related AE is still only grade 1), HCQ should be held. When myopathy/muscle weakness returns to grade ≤ 1 (or after holding for a period per MD discretion, as long as symptoms and lab values are trending back to normal), HCQ may be reintroduced at the next lower dose level. It is not necessary that CPK return to grade ≤ 1 to restart drug, so long as myopathy has. It is intended that close monitoring and implementing HCQ dose reduction at early signs of myopathy will prevent subjects progressively worsening to the point that they have to come off study drug (HCQ) altogether.

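### As written, the section 8.8 rule to modify only everolimus for every toxicity outside the overlapping list conflicts with the hydroxychloroquine rules in 8.8.1 and 8.8.1.1; the practical risk is small

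*Protocol*

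**What the plan says.** Protocol section 8.8 opens by allowing dose adjustment and notes that "Dose modification guidelines are found in the sections below". It permits physician discretion, which must be documented, and asks that departures from the guidelines be discussed in advance. It then turns to shared toxicities: "Because nausea, vomiting, diarrhea or rash may be attributable to either HCQ or EVE, Table 8 outlines the order" of reduction. The next sentence covers everything else: "All other toxicities should be managed with dose modification of EVE alone".

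Table 8 follows. Its title refers to overlapping toxicities, and its rows are rash, nausea, anorexia and diarrhea.

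The HCQ rules come next.
- Section 8.8.1: an event of grade 3 or higher "attributed as possibly, probably or definitely related to HCQ will result in the dose being held until the AE has resolved", "while EVE dosing may continue uninterrupted". HCQ then restarts at a reduced dose.
- Section 8.8.1, in bold: visual field deficit "should prompt drug discontinuation and ophthalmologic evaluation immediately".
- Section 8.8.1.1: HCQ is held "in the instance of grade >1 muscle weakness and/or elevated CPK or at MD discretion", and may restart at the next lower level once the weakness has improved.

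Section 8.8.2 ties EVE modification for non-hematological events to at least possible attribution to EVE.

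**The concern.** The 8.8 sentence is an operative dosing instruction. For an event caused by HCQ and not listed in Table 8, it names the other drug. A site that took it at its word would leave the suspected drug unchanged and alter the one not suspected. The population is potentially curable (section 12.2.1), so dosing rules should not point two ways.

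There is also a compliance question. Section 8.8 wants departures from its guidelines discussed beforehand and discretionary decisions recorded as such. With two opposing guidelines, it is unclear which action complies and which departs.

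**Working it through.** No arithmetic applies. The check sets the general sentence beside each specific rule.

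| Situation | 8.8 sentence, literally | Specific rule | Agree? |
|---|---|---|---|
| Grade 3 or higher, outside Table 8, at least possibly HCQ-related | Modify EVE only | 8.8.1: hold HCQ, restart lower; EVE may go on unchanged | No, opposite drug |
| Visual field deficit | Modify EVE only | 8.8.1: stop drug at once (in the HCQ section) | No, opposite drug |
| Suspected myopathy: weakness above grade 1, raised CPK, or physician judgement | Modify EVE only | 8.8.1.1: hold HCQ, restart lower | No, opposite drug |
| Outside Table 8, non-hematological, attributed to EVE only | Modify EVE only | 8.8.2 and Table 11: modify EVE | Yes |
| Known EVE hematological toxicity | Modify EVE only | 8.8.2: attributed to EVE, not HCQ | Yes |
| Arm A, first 24 weeks (section 7.1) | No EVE to modify | 8.8.1 and 8.8.1.1 | Sentence cannot apply |

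**Do these events fall under the general sentence?** Yes. Visual field deficit and myopathy are neither in the 8.8 lead-in nor in Table 8. Weakness shows how the conflict can arise on the combination: section 8.3 lists weakness for EVE, and section 8.2 lists myopathy with progressive weakness for HCQ. The general sentence then points to EVE and 8.8.1.1 to HCQ.

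**Is precedence stated anywhere?** Three places might supply it.
1. The pointer in 8.8 to later sections says where the rules are, not that they override the sentence.
2. Physician discretion in 8.8 allows a choice but sets no default.
3. Section 7.8 takes the patient off the drug most likely responsible, but only for a treatment-related delay of more than 28 days, not for the first dose decision.

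None of them settles the order.

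**Does a narrower reading remove the conflict?** Suppose the sentence is only a default for combination patients when the cause is unclear. Section 8.8.1 already acts when the relation to HCQ is merely possible. An event of uncertain cause at grade 3 or higher can therefore still call for an HCQ hold. The narrower reading shrinks the conflict but does not remove it.

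**A small mismatch in the same place.** The lead-in names vomiting but not anorexia. Table 8 has anorexia but not vomiting. Vomiting therefore has no stated order of reduction.

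**The case against.** The strongest reply is that context limits the sentence. It stands between a statement about shared attribution and a table for overlapping toxicities, so it can be read as choosing an agent when the cause is unclear. The rest of the scheme follows attribution: 8.8.1 acts on HCQ-related events, 8.8.2 on EVE-related ones, and 7.8 on the likelier culprit. A fully literal reading makes no sense in Arm A and would leave 8.8.1.1 without use in combination patients. The two most safety-critical HCQ events already have explicit instructions.

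Most of this stands. A narrower intent is likely, and it is why the practical risk is small. It does not show that the text is consistent: the limit has to be inferred, and the sentence carries no qualifier.

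The reply also disposes of a stronger reading. A reader might infer that a combination patient with a purely HCQ-caused event would have EVE cut while HCQ stayed at full dose, and might try to size the harm by comparing the dose steps in Tables 9 and 10. That outcome requires the introductory sentence to override both 8.8.1 and 8.8.2, since 8.8.2 conditions EVE changes for non-hematological events on attribution to EVE. The documents do not support that, so no such contrast is offered here.

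**Conclusion.** The inconsistency is real in the current text. For HCQ-attributed events outside Table 8, section 8.8 names one drug and 8.8.1 and 8.8.1.1 name the other, with no stated precedence. In Arm A during HCQ monotherapy the sentence cannot be followed.

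The size is small. That is a judgement, and it assumes that sites follow the specific sections over the general sentence. The documents give no frequency of misapplication, and none is estimated.

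A reader might also infer that feasibility results are at risk. The documents do not support this: the feasibility criterion in 12.2.1 (completing six cycles without grade 3 or 4 toxicity) and its analysis do not refer to which drug is modified. No effect on an endpoint, the sample size or any statistic is claimed. The point should be corrected because the correction is easy and favours patient safety, not because harm is expected.

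**What to change.** Replace the sentence in 8.8 with text to this effect:

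> In patients on the combination, a toxicity that is outside Table 8 and not attributed to HCQ is handled by changing the EVE dose only. A toxicity outside Table 8 that is at least possibly related to HCQ, including visual field deficit and suspected myopathy, is handled under 8.8.1 and 8.8.1.1; if it is also at least possibly related to EVE, 8.8.2 and Table 11 apply too. For toxicities in Table 8 on the combination, Table 8 decides which agent is modified first.

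The last sentence is needed. Without it, a grade 3 rash or diarrhea possibly related to HCQ would go to an HCQ hold under 8.8.1, while Table 8 reduces EVE first.

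Add anorexia to the lead-in so that it matches Table 8. Vomiting should not simply be merged into the nausea row, because that would set an HCQ-first order that the protocol does not state. Section 8.6.3 treats nausea and vomiting together only for supportive care. The investigator should specify the order.

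The cost is one sentence replaced by three, one word added and one order specified. Sample size, endpoints and analysis do not change. Under section 16.4 a non-administrative amendment needs ethics approval and review by the everolimus supplier, so the change can go in with the next amendment.
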